### 14.1.11 Duration of hospitalization and ICU stay

	Arm A [n (%)]	Arm B [n (%)]
No of days of hospitalization		
N	XX	XX
Mean (SD)	XX.X (XX.XX)	XX.X (XX.XX)
Median	XX.X	XX.X
Min, Max	XX, XX	XX, XX
No of days of hospitalization during study		
N	XX	XX
Mean (SD)	XX.X (XX.XX)	XX.X (XX.XX)
Median	XX.X	XX.X
Min, Max	XX, XX	XX, XX
No of days of ICU		
N	Xxx	Xxx
Mean (SD)	Xxx	Xxx
Median	Xxx	Xxx
Min, Max	Xxx	Xxx
No of days of ICU during study		
N	XX	XX
Mean (SD)	XX.X (XX.XX)	XX.X (XX.XX)
Median	XX.X	XX.X
Min, Max	XX, XX	XX, XX
Time to independence from non-invasive mechanical ventilation calculated in days		
N	Xxx	Xxx
Mean	Xxx	Xxx
Median	Xxx	Xxx
Min, Max	Xxx	Xxx
Duration in Days for independence from oxygen therapy		
N	Xxx	Xxx
Mean	Xxx	Xxx
Median	xxx	Xxx
Min, Max	xxx	Xxx

### 14.1.12 Summary of Study Treatment: Itolizumab treatment details in Arm A

	Arm A
Dose	
N	XX
Mean (SD)	XX.X (XX.XX)
Median	XX.X
Min, Max	XX, XX
No of infusion received during study	
1	XX (XX.X %)
2	XX (XX.X %)
3	XX (XX.X %)
4	XX (XX.X %)
Infusion interrupted	
Yes	XX (XX.X %)
No	XX (XX.X %)
Reason for interruption	
XXXX	XX (XX.X %)
XXXX	XX (XX.X %)
XXXX	XX (XX.X %)
Regimen administered	
Weekly	XX (XX.X %)
Alternate weekly	XX (XX.X %)
Dose deferred	
Yes	XX (XX.X %)
No	XX (XX.X %)
Reason	
XXXX	XX (XX.X %)
XXXX	XX (XX.X %)
XXXX	XX (XX.X %)

### 14.1.13 Summary of BSC treatment details in both arms

	Arm A n (%)	Arm B n (%)
Antibiotics		
XXXX	XX (XX.X %)	XX (XX.X %)
XXXX	XX (XX.X %)	XX (XX.X %)
XXXX	XX (XX.X %)	XX (XX.X %)
Antivirals		
XXXX	XX (XX.X %)	XX (XX.X %)
XXXX	XX (XX.X %)	XX (XX.X %)
XXXX	XX (XX.X %)	XX (XX.X %)
HCQ	XX (XX.X %)	XX (XX.X %)
Heparin	XX (XX.X %)	XX (XX.X %)
Glucocorticoids		
Supplements	XX (XX.X %)	XX (XX.X %)
IV fluids	XX (XX.X %)	XX (XX.X %)
Others		
XXXX	XX (XX.X %)	XX (XX.X %)
XXXX	XX (XX.X %)	XX (XX.X %)
XXXX	XX (XX.X %)	XX (XX.X %)

## 14.2 Primary outcome measures

### 14.2.1 Primary Outcome Measures

Visit*		Arm A (N=XX)	Arm B (N=XX)
Baseline	patients with Stable SpO2 without increasing FiO2	XX (XX.X %)	XX (XX.X %)
	patients with Stable PaO2 without increasing FiO2	XX (XX.X %)	XX (XX.X %)

\*day 7, day 14, day 21 and day 30/EOS or all available visits

### 14.2.2 Proportion of patients needed intubation during the study

	Arm A (N=XX)	Arm B (N=XX)
Patients needed intubation n(%)	XX (XX.X %)	XX (XX.X %)

### 14.2.3 Reduction in proportion of patients who need Non-invasive ventilation

Visit		Arm A (N=XX)	Arm B (N=XX)
	Patients on Non-invasive ventilation at baseline	XX	XX
Day 7	N	XX	XX
	Stable or improved (shifted to bag and mask, NRBM, FM, nasal canula or off O2)	XX (XX.X %)	XX (XX.X %)
Day 14	N	XX	XX
	Stable or improved (shifted to bag and mask, NRBM, FM, nasal canula or off O2)	XX (XX.X %)	XX (XX.X %)
Day 21	N	XX	XX
	Stable or improved (shifted to bag and mask, NRBM, FM, nasal canula or off O2)	XX (XX.X %)	XX (XX.X %)
Day 30/EOS	N	XX	XX
	Stable or improved (shifted to bag and mask, NRBM, FM, nasal canula or off O2)	XX (XX.X %)	XX (XX.X %)

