ALZUMAB™ should not be administered to patients having history of severe allergy or known hypersensitivity reaction to any component of ALZUMAB™ or any murine proteins. Additionally, ALZUMAB™ is contraindicated in patients with any active serious infection including tuberculosis and HIV-AIDS.

It is recommended that live/attenuated vaccines not be given concurrently with ALZUMAB™.

As with other IgG antibodies, itolizumab may cross the placenta during pregnancy. The available clinical experience is too limited to exclude a risk, and administration of ALZUMAB™ is therefore not recommended during pregnancy.

Infections and Reactivation of Tuberculosis

Physicians should exercise caution before and during Itolizumab Injection treatment in patients with a history of recurrent infections or underlying conditions which may predispose them to serious infections. Patients should be monitored closely for the development of signs and symptoms of infection during and after treatment with Itolizumab.

4. Objectives

Primary Objectives:

To study the efficacy and safety of adding Itolizumab in patients with Moderate to Severe COVID-19 complications (Cytokine Release Syndrome).

Secondary Objectives:

To study the effect of immunomodulation by Itolizumab and its correlation to clinical improvement by evaluating biomarker data (IL6, TNF-a, IL17, IL1, Interferon -A etc.) before and after Itolizumab treatment

5. Outcome Measures

Primary Outcome Measures:

1. Proportion of patients with deterioration of lung function as measured by*:
 - Stable SpO₂ without increasing FiO₂
 - Stable PaO₂ without increasing FiO₂
2. Reduction of endo-tracheal intubation rate, measured as rate of patients needing intubation*
3. Reduction in proportion of patients who need*
 - Non-invasive ventilation
 - Invasive mechanical ventilation
 - High flow nasal oxygen
4. Time of duration of mechanical ventilation or time to end of mechanical, measured as elapsed time from the start date of mechanical ventilation to the weaning date, for patients needing intubation*
5. One-month mortality rate between the two arms* [Time Frame: up to 1 month]

1-month mortality is defined as the ratio of patients who will live after 1month from study start out of those registered at baseline

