## **9 Efficacy Evaluation**

### **Primary Efficacy Evaluation**

Proportion of patients with deterioration of lung function as measured by Stable SpO2 without increasing FiO2 and Stable PaO2 without increasing FiO2 will be summarized using count and

percentage. The difference between two proportion with its 95% Confidence interval and associated p-values may be presented, if p-value is less than 0.05 it can be concluded that there is a statistically significant difference between two proportions.

Reduction of endo-tracheal intubation rate, measured as rate of patients needing intubation will be summarize using descriptive statistics.

Reduction in proportion of patients who need/ Non-invasive ventilation / Invasive mechanical ventilation/high flow nasal oxygen will be summarized using count & percentage.

One-month mortality rate between the two arms will be summarized. The difference between two rates with its 95% Confidence interval and associated p-values may be presented, if p-value is less than 0.05 it can be concluded that there is a statistically significant difference between two-rates.

Change in inflammatory markers like CRP (C-reactive protein) level, d-Dimer, ferritin etc will be summarize with descriptive statistics. Change from Baseline may be presented along with 95% CI.

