## **12 Key Definitions**

For few assessments (weight, physical examination, vital signs haematology, biochemistry Chest X Ray/CT scan), screening assessments will be considered as baseline assessment (as day 1).

Stable SpO2:

- Stable SpO2: Defined as absence of increase in FiO2 to maintain Spo2 ≥ 92%
- Improvement of SpO2: Defined as decrease in FiO2 to maintain SpO2 >92%

Stable PaO2:

- Stable PaO2: Defined as up to 10% change in PaO2/FiO2 ratio from baseline
- Improvement of PaO2: Defined as > 10% improvement in PaO2/FiO2 ratio from baseline (including patients weaned off oxygen)

If assessment is missing on particular day then it should be captured from assessment available in next two days.

For lab parameters, if assessment is missing on particular day, then it should be captured from assessment available in ± 2 days.

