### 14.2.6 Reduction in proportion of patients who need High Flow Nasal Oxygen

Visit		Arm A (N=XX)	Arm B (N=XX)
	Patients on High flow nasal oxygen at baseline	XX	XX
Day 7	N	XX	XX
	Stable or improved (off O2)	XX (XX.X %)	XX (XX.X %)
Day 14	N	XX	XX
	Stable or improved (off O2)	XX (XX.X %)	XX (XX.X %)
Day 21	N	XX	XX
	Stable or improved (off O2)	XX (XX.X %)	XX (XX.X %)
Day 30/EOS	N	XX	XX
	Stable or improved (off O2)	XX (XX.X %)	XX (XX.X %)

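### After baseline, Tables 14.2.3 and 14.2.6 do not show how many patients need NIV or high-flow oxygen, which are two of the three parts of primary endpoint 3

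*SAP*

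**What the plan says.** Protocol Section 5 and SAP 3.2.1 list as the third primary outcome "Reduction in proportion of patients who need" NIV, invasive mechanical ventilation or high-flow nasal oxygen. It applies to both arms, with no restriction by device at baseline. SAP Section 9 commits to a summary: "Reduction in proportion of patients who need/ Non-invasive ventilation / Invasive mechanical ventilation/high flow nasal oxygen will be summarized using count & percentage".

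The shells that carry this are:

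- **SAP 14.2.3 (NIV).** A baseline count, "Patients on Non-invasive ventilation at baseline". Then, at Days 7, 14, 21 and 30/EOS, an unlabelled N and one row, "Stable or improved (shifted to bag and mask, NRBM, FM, nasal canula or off O2").
- **SAP 14.2.6 (high-flow oxygen).** A baseline count, "Patients on High flow nasal oxygen at baseline". Then, at the same visits, an unlabelled N and one row, "Stable or improved (off O2").
- **SAP 14.2.2 (intubation).** Number and percentage needing intubation at any time in the study, by arm. Patients already on invasive ventilation are excluded at entry (SAP 4.4), so this table in effect covers the invasive-ventilation part.

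SAP Section 12 defines 'stable' twice. For SpO2 it is "Defined as absence of increase in" FiO2 at a saturation threshold. For PaO2 it is "Defined as up to 10% change in" the PaO2/FiO2 ratio. Neither definition refers to a device. The carry-forward rules in SAP Section 13 name only the lung-function endpoint, and SAP Section 6 bases percentages on non-missing values.

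**The concern.** The same word, need, is handled in two ways. For intubation the SAP counts everyone in the arm who needed it during the study. For NIV and high-flow oxygen it starts from patients already on the device and reports how they fared. Eligibility (SAP 4.3) does not require any device at entry, so patients can enter off NIV and start it later. Such a start is exactly the need that the endpoint is about.

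If the visit N is the baseline users, a new start appears nowhere in the table. A table carrying the endpoint's name would then report a different quantity. Its percentage would also depend on an undefined word, and on how deaths, intubations and discharges enter the N.

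**Working it through.** **1. Rows against endpoint (NIV; high-flow oxygen is analogous)**

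| Quantity | Row in the planned shells? |
|---|---|
| On device at baseline | Yes, count only |
| On device at a later visit | No |
| Ever on device after randomisation | No |
| Newly started | No |
| Stable or improved | Yes, pooled |

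Other tables do not fill the gap. Tables 14.2.1, 14.2.10, 14.2.11 and S5 reflect oxygenation, oxygen requirement or an ordinal score but do not identify the device. Table 14.1.11 gives days to independence from NIV with an undefined N, and has no high-flow row. Listing 16.1.12 holds delivery mode by patient, but it is a listing.

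**2. What a completed shell leaves open**

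The documents give no figure to reproduce, so this is a bounding count with assumed fills. About 30 patients at 2:1 (SAP 4.5) gives 20 v 10. Let n be the arm size, b the baseline NIV users and s those stable or improved at Day 7. Assume that all b are assessed.

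- If stable includes still being on NIV, and the other b − s have been intubated or died, patients on NIV at Day 7 range from 0 to s + (n − b). With n = 20, b = 4, s = 3: 0 to 3 + 16 = 19 of 20 (0% to 95%).
- If only the bracketed shifts count, the upper bound is (b − s) + (n − b) = 1 + 16 = 17 of 20 (85%).
- Ever on NIV ranges from b to n: 4 to 20 of 20 (20% to 100%).

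**3. Insensitivity to new starts**

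Assume that 4/20 v 2/10 are on NIV at baseline (20%), that half step down by Day 30 (2 v 1), that the other half stay on NIV, and that every new starter is still on NIV at Day 30. Take N as the baseline users.

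| New starters, A v B | On NIV at Day 30 | Any use | 14.2.3, bracketed shifts only | 14.2.3, stable includes unchanged |
|---|---|---|---|---|
| 0/16 v 0/8 | 2/20 v 1/10 (10%) | 4/20 v 2/10 (20%) | 2/4 v 1/2 (50%) | 4/4 v 2/2 (100%) |
| 2/16 v 1/8 (12.5%) | 4/20 v 2/10 (20%) | 6/20 v 3/10 (30%) | 2/4 v 1/2 (50%) | 4/4 v 2/2 (100%) |
| 4/16 v 2/8 (25%) | 6/20 v 3/10 (30%) | 8/20 v 4/10 (40%) | 2/4 v 1/2 (50%) | 4/4 v 2/2 (100%) |

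From 20% at baseline, NIV use falls, stays level or rises, and the table is the same each time. Arms can also differ unseen. Arm A from the first row with Arm B from the third gives 10% v 30% on NIV at Day 30, and the table still shows equal percentages.

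**4. Classification gaps**

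- *Still on the device.* Unchanged counts as favourable under one reading and not under the other: 100% against 50% above.
- *Step-down from high-flow oxygen.* 14.2.6 lists only coming off oxygen. A move to a non-rebreather mask, face mask or ordinary cannula has no stated category.
- *NIV to high-flow oxygen.* 14.2.3 lists nasal cannula without saying whether high-flow is included.
- *Death, intubation, discharge.* No rule for these tables says whether such a patient stays in the N.

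**5. Size of the subgroup**

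The baseline NIV share is not given. At an assumed 10% to 30%, the subgroup is 2 v 1 to 6 v 3, and one Arm B patient moves its percentage by 100 to 33 points.

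**The case against.** The strongest reply is that Section 9 is also part of the plan and promises a count and percentage of patients who need each support. Sections 6 and 13 allow further tables and data points, and Section 1 allows revision before database lock. The endpoint speaks of a reduction, and the shells carry that wording in their titles, so the sponsor may have meant step-down among users. The trial is small and has no formal sample size, and Section 9 plans no test or interval for this endpoint.

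Much of that stands, and it limits the point:

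- A reader might infer that the shells have no row at all for patients on these devices. They do, at baseline.
- A reader might infer that the NIV and high-flow parts are left without any planned analysis. Section 9 plans one; the shells do not display it.
- A reader might infer that nothing about a reduction can be read. If N is the baseline users and the bracket defines the category, their step-down can be read directly.
- A reader might infer that the layout favours itolizumab. Nothing in the documents fixes a direction.

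What does not stand is the permission clause as an answer. It commits to nothing. In an open-label trial, the summary of a primary endpoint should not be chosen once data are in view.

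**Conclusion.** The point holds for the tables after baseline. Whole-arm need for NIV and high-flow oxygen, promised in Section 9, is not shown in the planned shells; at most a step-down among baseline users is. Invasive ventilation is in effect covered by 14.2.2.

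The absence of the rows is certain from the shells. That the table is blind to new starts rests on reading the unlabelled N as the baseline users, which is likely but not stated. The counts in the working are assumed and show only how much the shell leaves open; they do not estimate the effect on this trial. This is a reporting gap that should be fixed. It does not invalidate the design.

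**What to change.** Before database lock, add to SAP 14.2.3 and 14.2.6, by arm over the whole analysis population:

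1. Number and percentage on the device at baseline and at each visit, with death, intubation and discharge as separate categories.
2. Number and percentage with any use from randomisation to Day 30.
3. Number and percentage newly starting after randomisation among those not on the device at randomisation. Use device status at randomisation in both arms. The SAP Section 8 baseline will not serve: in Arm A it is the last value before first dose, so a patient who starts NIV between randomisation and first dose would drop out of the denominator.

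Keep the step-down tables as supportive. In them, label N as baseline users assessed at the visit, give unchanged and improved separate rows, and list every device transition. Include high-flow oxygen to non-rebreather mask, face mask or cannula, and switches in either direction between NIV and high-flow oxygen. Put the device meaning of stable in SAP Section 12.

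The cost is a few descriptive rows, imprecise at about 20 v 10, and one definition. No new data are needed if the delivery-mode field in Listing 16.1.12 separates NIV from high-flow oxygen. The listing shows no categories, so this must be checked first.

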### 14.2.4 Reduction in proportion of patients who need NRBM

Visit		Arm A (N=XX)	Arm B (N=XX)
	Patients on NRBM at baseline	XX	XX
Day 7	N	XX	XX
	Stable or improved (shifted to FM, nasal canula or off O2)	XX (XX.X %)	XX (XX.X %)
Day 14	N	XX	XX
	Stable or improved (shifted to FM, nasal canula or off O2)	XX (XX.X %)	XX (XX.X %)
Day 21	N	XX	XX
	Stable or improved (shifted to FM, nasal canula or off O2)	XX (XX.X %)	XX (XX.X %)
Day 30/EOS	N	XX	XX
	Stable or improved (shifted to FM, nasal canula or off O2)	XX (XX.X %)	XX (XX.X %)

### 14.2.5 Reduction in proportion of patients who need Face Mask

Visit		Arm A (N=XX)	Arm B (N=XX)
	Patients on FM at baseline	XX	XX
Day 7	N	XX	XX
	Stable or improved (shifted to nasal canula or off O2)	XX (XX.X %)	XX (XX.X %)
Day 14	N	XX	XX
	Stable or improved (shifted to nasal canula or off O2)	XX (XX.X %)	XX (XX.X %)
Day 21	N	XX	XX
	Stable or improved (shifted to nasal canula or off O2)	XX (XX.X %)	XX (XX.X %)
Day 30/EOS	N	XX	XX
	Stable or improved (shifted to nasal canula or off O2)	XX (XX.X %)	XX (XX.X %)

### 14.2.6 Reduction in proportion of patients who need High Flow Nasal Oxygen

Visit		Arm A (N=XX)	Arm B (N=XX)
	Patients on High flow nasal oxygen at baseline	XX	XX
Day 7	N	XX	XX
	Stable or improved (off O2)	XX (XX.X %)	XX (XX.X %)
Day 14	N	XX	XX
	Stable or improved (off O2)	XX (XX.X %)	XX (XX.X %)
Day 21	N	XX	XX
	Stable or improved (off O2)	XX (XX.X %)	XX (XX.X %)
Day 30/EOS	N	XX	XX
	Stable or improved (off O2)	XX (XX.X %)	XX (XX.X %)

### 14.2.7 One-month Mortality Rate

	Arm A [n (%)]	Arm B [n (%)]
Number of patients died	XX (XX.X %)	XX (XX.X %)
95% CI Difference between Rate	XX (XX , XX)	
p-value	XX	

### 14.2.8 Change in inflammatory markers before and after dosing in Treatment ARM A

	Before dose	12-24 hrs after dosing
Serum ferritin		
First dose (n)		
Mean change		
Second dose (n)		
Mean change		
Third Dose (n)		
Mean change		
Fourth Dose (n)		
Mean change		
Programming Note: Repeat for other inflammatory markers: Serum LDH, Serum CRP, Serum d-Dimer etc		
Repeat Table for first , second, third and fourth infusion (dose) of Itolizumab		

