## 3.2 Outcome Measures

### 3.2.1 Primary endpoint

1. Proportion of patients with deterioration of lung function as measured by\*:
  - Stable SpO2 without increasing FiO2
  - Stable PaO2 without increasing FiO2
2. Reduction of endo-tracheal intubation rate, measured as rate of patients needing intubation\*
3. Reduction in proportion of patients who need\*
  - Non-invasive ventilation
  - Invasive mechanical ventilation
  - High flow nasal oxygen
4. Time of duration of mechanical ventilation or time to end of mechanical, measured as elapsed time from the start date of mechanical ventilation to the weaning date, for patients needing intubation\*
5. One-month mortality rate between the two arms\* [ Time Frame: up to 1 month ] 1-month mortality is defined as the ratio of patients who will live after 1 month from study start out of those registered at baseline
6. Change in inflammatory markers like CRP (C-reactive protein) level, d-Dimer, ferritin etc. [ Time Frame: Arm A; baseline, during treatment (Before every dose and 12 to 24 h after every dose) up to 1 month, Arm B: baseline, 12 to 24 h and approx. 7 and 14 days after randomization ]

\* Applicable for both the arm

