## **6 General Aspects for Statistical Methods**

In general, metric variables and derived parameters will be presented using descriptive summary statistics including arithmetic mean, standard deviation, median, minimum and maximum.

Categorical variables will be presented using descriptive summary statistics including number of patients and percentages. Percentages of patients will be based on non-missing values. The presentation will be by treatment group. Individual values as well as minimum and maximum will be presented with the same number of decimal places as the raw data. Derived parameter will have as many decimal places as the measured number with the smallest number of decimal places. Descriptive statistics, such as arithmetic/geometric mean and median will be presented with an additional decimal place and standard deviation with two additional decimal places as the raw or derived data. All relevant subject data will be included in the listings; and all subjects entered into the database will be included in subject data listings. SAS 9.4 or any other validated software will be used for analysis purpose and generating Tables, Listings & Figures. P-values less than 0.05 may be reported as statistically significant.

The formatting of the final version of a table, figure, or listing may differ from what is presented in the mock shell or the presentation of the results may be changed, however the key content will remain unchanged. Additional tables, figures, and listings may be generated to supplement the planned output.

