### **Secondary Efficacy Evaluation**

Biomarkers (IL-6, TNF-a, IL1, IL17, etc...) will be summarize using summary statistics.

Lymphocyte count will be summarized using count & percentage.

PaO2 (partial pressure of oxygen) / FiO2 (fraction of inspired oxygen, FiO2) ratio (or P/F ratio) calculated from arterial blood gas analyses. Radiological response will be summarized in descriptive manner.

Duration of hospitalization will be summarized using descriptive statistics.

Time to independence from non-invasive mechanical ventilation and from oxygen therapy will be summarize using summary statistics.

Biomarkers (IL-6, TNF-a, IL1, IL17, etc...) Lymphocyte count, CRP (C-reactive protein) level, PaO2 (partial pressure of oxygen) / FiO2 (fraction of inspired oxygen, FiO2) ratio (or P/F ratio), will be summarized with descriptive statistics. Change from Baseline will be presented along with 95% CI for the difference between two treatments will be reported.

Radiological response, Duration of hospitalization & Remission of respiratory symptoms will be summarized using descriptive statistics.

Number of participants with treatment-related side effects as assessed by Common Terminology Criteria for Adverse Event (CTCAE) version 5.0 graded according to CTCAE criteria (v5.0) will be summarized based on frequency and proportion of total subjects, by system organ class and preferred term. Proportion of subjects with IRR in both the arm will be presented. An overall summary of deaths will be presented by treatment arms.

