### **Laboratory Evaluations**

For haematology and biochemistry variables, descriptive summaries of observed values and changes from baseline will be presented by treatment arm. Numerical variables will be described by number of subjects, mean, standard deviation, median, minimum and maximum and categorical variables will be described by number and percentage.

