### Graphs

- Figure 1: Disposition by centres: Bar Graph
- Figure 2: PaO2/FiO2 ratio: Line Graph
- Figure 3: change from baseline for Key Lab parameters: Ferritin, d-dimer, LDH, CRP, Lymphocyte counts
- Figure 4: KM Curve for time to event endpoints

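### Primary endpoint 6 (CRP, d-dimer, ferritin): its only shell in SAP 14.2 is an uncontrolled Arm A before/after change, no between-arm contrast is specified for ferritin or d-dimer, and the one promised for CRP has no shell

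*SAP*

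**What the plan says.** - **Endpoint and sampling.** SAP 3.2.1 (and Protocol 5) list change in CRP, d-dimer and ferritin as item 6 of the primary outcomes. Arm A is sampled "Before every dose and 12 to 24 h after every dose" for up to a month. The control schedule is "Arm B: baseline, 12 to 24 h and approx. 7 and 14 days after randomization".
- **Primary analysis text.** SAP 9 says of these markers: "d-Dimer, ferritin etc will be summarize with descriptive statistics. Change from Baseline may be presented along with 95% CI". The same section does mention a difference between arms, with interval and p-value, for lung function and mortality.
- **Secondary analysis text.** SAP 9 lists CRP again, with the cytokine biomarkers, lymphocyte count and P/F ratio, and says: "Change from Baseline will be presented along with 95% CI for the difference between two treatments will be reported". Ferritin and d-dimer are not named there.
- **Shell for endpoint 6.** SAP 14.2.8 is headed "Change in inflammatory markers before and after dosing in Treatment ARM A". It has columns for before dose and 12-24 h after dosing and a mean change per infusion, for ferritin and then LDH, CRP and d-dimer. It has no Arm B column and no interval.
- **By-arm description elsewhere.** SAP 6 says "The presentation will be by treatment group", and SAP 10 says of haematology and biochemistry that "descriptive summaries of observed values and changes from baseline will be presented by treatment arm". Shell 14.1.9 has Arm A and Arm B columns for ferritin, d-dimer and LDH, with change from baseline. CRP could enter it only under its closing etc. The graph list has "Figure 3: change from baseline for Key Lab parameters: Ferritin, d-dimer, LDH, CRP, Lymphocyte counts", without saying whether arms are shown.
- **Premedication.** Protocol 7 gives hydrocortisone (or an equivalent) before infusions in Arm A only.

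**The concern.** In a randomised trial the control arm is there to show what would have happened without the drug. For this endpoint the control samples are planned, but the primary-outcome table does not use them. A fall in CRP or ferritin after an infusion can come from itolizumab, from the natural course or supportive care, or from the glucocorticoid given just beforehand. Table 14.2.8 shows the sum of the three.

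SAP 4.1 calls the trial pivotal. If the plan is followed as written, the report will carry an uncontrolled change under the primary heading. Any comparison of arms for ferritin or d-dimer would then have to be chosen after the data are seen.

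**Working it through.** The documents give no effect size, SD or power for these markers, so there is no planned figure to reproduce. The check has two parts.

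**1. Text against shells**

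| Marker | Between-arm contrast in SAP 9 | Shell with both arms | Shell with a between-arm interval |
|---|---|---|---|
| Ferritin | none | 14.1.9, descriptive | none |
| d-dimer | none | 14.1.9, descriptive | none |
| CRP | none in the primary text; 95% interval in the secondary text | not named (14.1.9 only through its etc.) | none |

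The only shell anywhere with a between-arm interval is 14.2.7, mortality. No other shell in 14.2 is planned for one arm; 14.2.9 heads both columns Arm A, evidently a slip.

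**2. Illustration of size**

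*From the documents:* about 30 patients at 2:1 (SAP 4.5), so 20 v 10; two-sided 5% (Protocol, Statistical Analysis).

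*Assumed:* normal data with equal SD at both times, in units of that SD; correlation rho of 0.3, 0.5 or 0.7 between baseline and follow-up; no drug effect; a fall f shared by both arms.

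(a) *Arm A interval alone, change from baseline to about day 7.* The SD of the change is √(2(1−rho)). The interval lies wholly below zero when the paired t statistic is under −2.093 (19 df). Its noncentrality is −f√20/√(2(1−rho)). For f = 0.3 and rho = 0.5 this is −0.3 × 4.472/1 = −1.342, which gives 24.6%.

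| Shared fall | rho 0.3 | rho 0.5 | rho 0.7 |
|---|---|---|---|
| 0.3 SD | 18.9% | 24.6% | 37.6% |
| 0.5 SD | 43.4% | 56.4% | 78.2% |

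(b) *Same rate of fall over the interval of 14.2.8.* Taking 0.3 to 0.5 SD as a linear fall over 7 days, 12 h at the slower rate is 0.3 × 0.5/7 = 0.021 SD and 24 h at the faster rate is 0.5 × 1/7 = 0.071 SD. The same formula gives 3.0% to 5.8% across the three correlations.

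(c) *Arm A v Arm B, ANCOVA on baseline.* With randomisation intact and no premedication effect, a 95% interval lies wholly below zero in 2.5% of trials whatever the shared fall. The half-width is roughly 2.052 × √((1−rho²)(1/20 + 1/10)) = 0.76, 0.69, 0.57 SD for rho 0.3, 0.5, 0.7. Simulation with 40,000 replicates gives 0.765, 0.693, 0.573. With 30% missing (14 v 7) the simulated values are 0.94, 0.85, 0.70 SD.

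(d) *On the ratio scale.* If the SD of the log marker is 0.6 to 1.0 (assumed) and rho is 0.5, the A/B ratio is known to within a factor of exp(0.693 × 0.6) = 1.5 to exp(0.693 × 1.0) = 2.0.

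**The case against.** **Arm B is not ignored.** Shell 14.1.9 shows ferritin, d-dimer and LDH by arm with n, mean, SD and change from baseline, including a 12-24 h row. A reader could compute an unadjusted difference from it. This stands, and a reader who inferred from 14.2.8 that control values are never tabulated would be wrong. But 14.1.9 sits outside the primary-outcome tables and carries no contrast.

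**CRP already has a contrast.** True in the secondary text of SAP 9, so it would be wrong to say that no CRP comparison is planned. What is missing is a shell, and agreement with the primary text. Shells are incomplete elsewhere too: 14.2.1 has no row for the lung-function difference. A missing shell is therefore weak evidence that the CRP analysis will not be done.

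**Extra tables are allowed** (SAP 6 and 13). They are, but the permission does not pre-specify a contrast. Reading ferritin into the etc. of the secondary biomarker list is possible but weak, because SAP 3.2.1 and 9 name it separately as an inflammatory marker.

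**Item 6 lacks the asterisk for both arms.** It nevertheless states Arm B sampling times.

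**The trial is small and exploratory.** SAP 4.5 has no formal sample size, and SAP 9 also treats intubation and ventilation descriptively. This limits the weight of the point and argues for estimates, not tests.

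**The 19% to 78% might be read as the error rate of 14.2.8.** The documents do not support that. The shell covers 12-24 h and has no interval, and over that span the same rate of fall gives about 3% to 6%. The larger figures need the optional interval of SAP 9, a change to about day 7, and a reader who looks at Arm A alone although SAP 6 presents results by group.

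**Conclusion.** The gap in the text is clear. A primary endpoint sampled in both arms has only an Arm A before/after shell in 14.2, ferritin and d-dimer have no specified contrast, and the CRP interval has no shell. Confidence in that is high.

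Confidence in the size is low. Every figure rests on assumed correlations and trends, and the 2.5% comparator also needs intact randomisation and no premedication effect. Neither is assured: SAP 7 requires a full dose for ITT/FAS in Arm A only, and SAP 4.5 replaces Arm A patients who do not complete the first infusion. Those matters affect the whole trial and belong in separate points.

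Because descriptive by-arm data are planned, this is a minor correction that should be made. It does not invalidate the plan.

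**What to change.** Add one both-arm table to SAP 14.2 for CRP, ferritin and d-dimer (LDH optional) at baseline, 12-24 h, day 7 and day 14, with n per arm and the numbers dead or discharged at each time.

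- Give the A v B difference with 95% interval, adjusted for baseline; for example, the ratio of geometric means from an ANCOVA of log marker on arm and log baseline.
- Name one main time in advance, for example day 7 counted from randomisation in both arms. Report the other times as estimates without significance claims.
- Make the primary and secondary text of SAP 9 agree on CRP.
- Label 14.2.8 supportive and uncontrolled, and state that the contrast is itolizumab plus premedication against supportive care.
- Footnote the Arm A full-dose requirement, the replacement rule, and the differing 12-24 h clocks (from dosing in Arm A, from randomisation in Arm B).

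**Cost.** SAP wording, one table, and 3 markers × 3 post-baseline times = 9 models (12 with LDH). No new samples are needed: Protocol 8.1 schedules CRP and biochemistry at every visit without restriction by arm. Intervals will be wide. Day 7 and day 14 will be available-case estimates after death or early discharge, possibly biased if these differ by arm, and should be labelled so. The table cannot remove the premedication effect.
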